6.2 Analysis Methods

Analysis of Primary estimand (ATE): A Treatment Policy Analysis

Unadjusted summary statistics of the PROMIS scores will be displayed by treatment allocation using means and standard deviations. A multivariate linear mixed-effects regression model using repeated measures (level 1) nested within participants (level 2) will then be used to compare the treatment groups including all available data on randomised participants, at all-time points up to and including 12 months [28]. The model will include fixed effects to adjust for the minimisation factor used by the randomisation system: initial elbow dislocation status, and fixed effects for age and gender. A treatment by time interaction (as a categorical variable) will be included. The random part of the model will include random intercept terms for centres (level 3) and the individual participant (level 2) to account for the dependence of observations of participants within the same centre and observations within the same participant over time. At the individual participant level, it will also include a random coefficient for the effect of time (measurement occasion) and an unstructured covariance structure for the association between the random intercept and occasion as shown in the equations below describing the functional relationship between the outcome indexed by centre, individual participant and measurement occasions:

$$Y_{c,i,t} = \alpha_{c,i} + \beta_i Time_i + \theta Treatment_i + \gamma Treatment_i Time_i + \delta_k Covariate_{k,i} + \varepsilon_{i,t}$$

where c index centres, i individual participants and t measurement occasion (e.g. baseline, 1^{st} , 2^{nd} and 3^{rd} follow-up visit) and $Time_i$ is a variable representing the time elapsed between randomisation and PROMIS questionnaire completed.

 θ denotes the overall treatment effect and γ the interaction of treatment by time and covariates will be the stratification factors used in the randomisation protocol.

Note: Care needs to be taken to code observation occasions appropriately. Ideally, the exact timing of outcome measurement relative to the timing of randomisation will be used and if observation timings are highly unbalanced over time, time covariates will be centred around the mean time for fitting.

The random part of the model, partitions the variance to centre-level, individual participant and observation level and completes the model specification as follows:

Centre-level random effects

$$\alpha_{c,i} = \alpha_0 + u_{a,c} + u_{\alpha,i}$$

where $u_{a,c} \sim Normal(0, \sigma_{centre}^2)$ quantifying between centre variation in baseline means and α_0 denoting the overall baseline mean

Individual participant-level random effects:

$$\beta_i = \beta_0 + u_{\beta,i}$$

$$\begin{pmatrix} u_{\alpha,i} \\ u_{\beta,i} \end{pmatrix} = MVN\begin{pmatrix} \sigma_{\alpha}^2 & \sigma_{\alpha,\beta} \\ \sigma_{\alpha,\beta} & \sigma_{\beta}^2 \end{pmatrix}$$

MVN denotes a multivariate normal distribution quantifying the between-individual variation in means and linear change over time, respectively along with their correlation and $\varepsilon_{i,t} \sim Normal(0, \sigma_{i,t}^2)$ the residual observational level variance.

This will be compared with a model assuming independence between the random intercept and slope with respect to reductions in the likelihood function and the precision of the estimate for the random slope.

Non-linearity for the effect terms will also be considered using restricted cubic splines in the fixed part of the model. Even when highly non-linear patterns are evident, the limited number of measurement occasions— only five, including the baseline—restricts the complexity needed for an adequate fit. This means that we will need at most 2-3 knots, which should be positioned at the centiles of the time axis distribution [29] and choosing the model with the smallest deviance and the simplest functional form for the effect of time in the fixed part of the model, will be used after considering a maximum of three models: (a) linear (b) cubic spline with 2 knots (c) cubic spline 3 knots.

Sites with less than 5 participants will be grouped together to allow reliable estimation [30, 31].

The adjusted mean differences (treatment effect) will be presented, along with 95% confidence intervals and p-values.

As a supporting analysis to check model assumptions, a simple analysis of covariance (ANCOVA) of the primary outcome at 12 months will also be presented, adjusting only for the baseline PROMIS score, following protocol analysis specifications.

Model Checking and normalising transformations: Assumptions of normality will be assessed graphically looking at residual and quantile-quantile (QQ) plots, and data transformation will be considered if model assumptions (particularly normality of residuals) are clearly violated. Mixed-effects models are robust to small deviations from normality in the residuals; however, if approximate normality cannot be achieved the data normalising transformations will be considered and then proceed fitted the same mixed effects linear model described above on the transformed scale. We will use the logistic transformation which is a transformation recommended for bounded outcomes [32]. Data will be first transformed to a (0, 1) scale (transformed y_new=(γ -min(γ))/(max(γ)-min(γ)), where γ represents the outcome), following Smithson et al [33] and using the logistic transformation, in line with the bounded nature of the measurement scale. Treatment effect estimates will be presented on the original scale by post-estimation back transforming.

Examination of residuals following model fitting will be undertaken including exploration of dependencies with observed covariates. Consideration will be given to augmenting the model to heteroscedastic (level 1) residuals especially when the model is fitted in the original scale, where strong patterns are observed between residual errors and covariates and variance increases with the mean [34]. It is expected that normalising transformation using the logistic transform will have a variance stabilising effect on the fitted model and

maybe preferable as it would result to a simplified model. Comparison of the log-likelihood values of a small number of competing models will be used to decide whether model (higher log-likelihood values indicate a better fitting model).

Outcomes measured in certain subgroups only: The secondary outcome DASH Sports/Performing arts module is only completed if the participant indicates regular participation in sport or musical activities. The analysis of this secondary outcome, **targeting the average treatment effect in the subgroup completing the DASH Sports/Performing arts module**, will use the same methods described for the primary outcome but augmented with propensity score weighting. As this subgroup is exclusively observed among participants engaged in sports and musical activities, this could probably lead to imbalances in covariates between the comparison groups. The propensity weighting scheme is selected because it maximises the efficiency of the estimate and provides an unbiased estimate of the subgroup average treatment effect due to randomisation. [35, 36]. The inverse probability treatment weighting (IPTW) scheme for the propensity of receiving the randomised treatment will be modelled as a function of baseline covariates including subgroup membership, age, sex, stratification factors, initial dislocation status, mechanism of injury, baseline pain score. All interactions between group membership and the rest of the baseline covariates will be included in this adjustment set [37].

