3.2 Randomisation and Blinding

Patients will be randomised after consent. All hospital treatment areas have access to the internet so will access the randomisation service in real time i.e. there will be no delay in patient treatment.

Consenting participants will be allocated randomly (1:1) to either operative fixation or non-surgical treatment. Randomisation will be performed using a minimisation algorithm to ensure balanced allocation of participants across the two treatment groups, stratified by centre and dislocation status of the elbow at presentation in the emergency department (i.e. dislocated or not dislocated). The first 30 participants will be randomised using a simple randomisation schedule produced by the trial statistician, to seed the minimisation algorithm, and a non-deterministic probabilistic element will be introduced to prevent predictability of the treatment allocation.

Stratification by centre within the minimisation algorithm will help to ensure balanced treatment assignment within centre so that any unobserved factors (e.g. case-mix) contributing to between-centre variation in practices are balanced between treatment arms. The catchment area (the local population served by the hospital) will be similar for all hospitals; each hospital being a children's injury unit dealing with these fractures on a regular basis. All of the recruiting hospitals, and indeed all hospitals throughout the NHS, use these techniques as part of their normal practice i.e. staff will already be equally familiar with both forms of treatment. This cannot eliminate the clinician-specific effect of an individual at any one centre. However, since the procedures are commonplace across the NHS, many clinicians will be involved in the management of this group of patients; likely between 5 and 20 clinicians at each centre, including consultants and trainee surgeons. Therefore, we anticipate that each individual clinician will only treat a handful of those enrolled in the trial, reducing the risk of a clinician-specific effect upon the outcome in any one centre.

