3.3 Sample Size

Extremity Score for Children. Raw scores are translated into standardised T scores with a population mean of 50 and a Standard Deviation (SD) of 10. The 'Minimally Clinically Important Difference' (MCID) for the PROMIS Upper Extremity Score amongst children with milder forms of disability has been demonstrated to be three to

four [11], we seek to find a difference of four points. Assuming a SD of 10, a total of 266 patients (133 in each arm) is required to provide 90% power at the 5% level (two-sided) to detect a 4-point difference between the groups. Allowing for a conservative 20% loss to follow-up, we plan to recruit 334 patients in total for this trial (167 per arm).

The SD of 10 derived by PROMIS was based on a sample of children with a higher proportion of chronic illness than the general population [12], and it is anticipated that the variation in outcomes in the treatment of acute medial epicondyle fractures is likely to be less than in a chronic illness.

Independent verification of the sample size is available in

Z:\CSM_SCIENCE\Statistical Analysis\4. Sample Size**SCIENCE_SampleSize_Verification_04Apr2019.docx**, stored in the confidential statistical section of the TMF.

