6.1 Outcome Definitions

Primary Outcome PROMIS Upper Extremity: measured pre-randomised (baseline), 4 weeks (routine follow-up) and then at 6 weeks, 3 months, 6 months and 12 months via electronic collection.

The primary outcome for this study is the functional recovery assessed using the Patient Report Outcomes Measurement Information System (PROMIS Bank v2.0: Upper Limb Score for Children Computer Adaptive Test (CAT) – PROMIS is a collection of patient-reported health status tools available for children and adults that were developed to be disease non-specific in collaboration with the USA National Institute for Health [20, 21]. This is a bounded score on a standardised scale (T-score) in the interval [10 – 58] (https://www.healthmeasures.net/images/PROMIS/manuals/Scoring_Manual_Only/PROMIS_Physical_Funct ion_User_Manual_and_Scoring_Instructions_05Dec2023.pdf). These tools can be administered to healthy children, as well as to children with a variety of chronic health conditions. They are generally self-reported from the age of eight years, and proxy-reported below eight years. The PROMIS Paediatric item banks were developed using a strategic item generation methodology adopted by the PROMIS Network using item response theory. Field-testing occurred among 4,129 children aged eight to 17 years old [22]. All raw scores generated from PROMIS instruments are translated into standardized T-scores with a population mean of 50 and a standard deviation (SD) of 10. The population mean refers to the mean of the calibration sample, which, for paediatric and parent proxy instruments, is composed of a higher percentage of patients with chronic illness. Lower T scores indicate a worse outcome for upper limb function. PROMIS is available in full (30 questions), short-form (eight questions), or as a computer adaptive test 'CAT' (average eight questions). A CAT

enables the answer from one question to inform the choice of the next so that each child completing a CAT could answer a distinct set of questions to arrive at their score.

Secondary Outcomes

Sport/Performing Art Module of DASH: measured pre-randomised (baseline), 4 weeks (routine follow-up) and then at 6 weeks, 3 months, 6 months and 12 months via electronic collection.

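### SAP 6.2: the logit fallback for the primary outcome is undefined at the scale limits as printed, and its log-likelihood rule, on the natural reading, compares scales without a Jacobian term

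*SAP*

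**What the plan says.** SAP 6.1 describes the primary outcome: "This is a bounded score on a standardised scale (T-score) in the interval" 10 to 58, both ends included. SAP 6.2 fits a linear mixed model to all visit records up to 12 months. It checks residuals graphically and considers a transformation if normality is clearly violated.

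The fallback has three steps:

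- **Rescaling.** "Data will be first transformed to a (0, 1) scale", by subtracting the minimum and dividing by the range, with a citation for the method. No endpoint adjustment is printed. The SAP does not say whether minimum and maximum are the scale limits or the sample extremes.
- **Refit and report.** The same model is fitted to the logit. "Treatment effect estimates will be presented on the original scale by post-estimation back transforming".
- **Choice of model.** After discussing a heteroscedastic model on the original scale and a simpler model on the logit scale, the section says: "Comparison of the log-likelihood values of a small number of competing models will be used to decide whether model". The sentence is incomplete. A parenthesis adds that a higher value means a better fit.

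Table 1 defines the effect as a mean difference in T-score at 12 months among all randomised participants. Protocol 10.1 names a different fallback for non-normal data: unadjusted non-parametric tests.

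**The concern.** The formula does not deliver the open interval that the SAP names. A record at 58 becomes exactly 1 and one at 10 becomes exactly 0, and neither has a logit. A pile-up of recovered children at the ceiling is also a likely reason for residual plots to look non-normal. The fallback is therefore most likely to be invoked where the printed formula fails most often. If boundary records drop out, the loss depends on the outcome and is greater in the better arm, so it pulls the estimate towards zero.

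The second problem is separate. Log-likelihoods of a model for y and a model for logit(y) are in different units. Comparing them directly rewards the change of units, so the choice of scale for the primary result could rest on a number that says little about fit.

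**Working it through.** **Plan's own figure.** Inputs from SAP 3.2 and 3.3: "Consenting participants will be allocated randomly (1:1) to either operative fixation or non-surgical treatment"; "Assuming a SD of 10, a total of 266 patients (133 in each arm) is required to provide 90% power at the 5% level"; "we seek to find a difference of four points"; "Allowing for a conservative 20% loss to follow-up, we plan to recruit 334 patients in total for this trial (167 per arm"). The normal approximation gives n = 2(1.960 + 1.282)² × 10²/4² = 131.3, so 132 per arm. The noncentral t gives 133 per arm (power 0.901). Then 133/0.8 = 166.25, so 167 per arm and 334 in total. The sample size reproduces, and 133 per arm is used below.

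**1. The limits.** With limits 10 and 58, p = (y − 10)/48.

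- y = 50 gives p = 0.833, logit 1.61.
- y = 57 gives p = 0.979, logit 3.85.
- y = 58 gives p = 1, logit undefined. y = 10 gives p = 0, logit undefined.

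If minimum and maximum are sample extremes, at least one record at each end is always undefined.

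**2. Possible size.** The share at 58 is not in the documents. Assumption: 12-month scores are normal and cut at 58, so the share at the ceiling is 1 − Φ((58 − mean)/SD). This is a single-visit comparison with 133 per arm, with boundary records dropped.

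| Assumed means, SD | Share at 58 | Difference, all records | Difference, boundary dropped | Power, all records | Power, logit with boundary dropped |
|---|---|---|---|---|---|
| 50 v 54, SD 10 | 1 − Φ(0.8) = 21% v 1 − Φ(0.4) = 34% | 2.9 | 2.0 | about 86% | about 43% |
| 45 v 49, SD 6 | 1 − Φ(2.17) = 1.5% v 1 − Φ(1.5) = 6.7% | 3.85 | 3.40 | above 99% | above 99% |

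The SAP's model uses all visits, so other visits partly make up for a lost 12-month record. A small five-visit simulation of the first case (random intercept, 60 runs, assumed distributions) moved the estimate from 2.98 to 2.37 and power from 83% to 70%. With 60 runs the power figures are rough: the standard error at 70% is √(0.7 × 0.3/60) ≈ 6 points.

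With an endpoint squeeze, p* = (p(N − 1) + 0.5)/N, no record is undefined. Single-visit power in the first case is then about 85%.

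**3. The likelihood rule.** With z = logit(p), dz/dy = 1/[48p(1 − p)]. The log-likelihood on the T-score scale is the logit-scale value minus Σ log[48p(1 − p)]. Without that term each record gives the logit log[48p(1 − p)] units:

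- y = 30: p = 0.4167, gain 2.46.
- y = 50: p = 0.8333, gain 1.90.
- The gain is positive for any y between 11.02 and 56.98.

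For 266 records at 1.90 to 2.46 each, that is 505 to 654 units. Simulated single-visit data (n = 266) agree: the mean advantage was 372 to 647 units. The uncorrected rule chose the logit in 100% of runs in all 12 main scenarios, six of them normal on the T-score scale. With the Jacobian, the logit was chosen in 0% to 33% of runs in those six.

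In a five-visit mixed model without a ceiling, mean log-likelihoods were −3942 (T-score), −1909 (logit, uncorrected) and −4640 (logit, corrected), so the ranking reverses. The uncorrected rule failed to choose the logit every time only with an endpoint squeeze and an extreme ceiling: 0% of runs at a T-score SD of 1.2 and 85% at 1.6.

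Dropped records distort the comparison further, because the two likelihoods then cover different data.

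**The case against.** The case for the SAP is substantial. It does not say that boundary scores are dropped. It names an open interval and cites a method, so an endpoint correction may be intended, and SAP 6.3 says that all collected data will be used. The only ceiling statement in the documents (Protocol 6.3, in a congenital limb population) is that the adaptive test showed no ceiling effect. Both documents expect an SD below 10. The selection sentence is incomplete and follows text on heteroscedastic residuals, where a comparison on one scale is valid. A graphical check comes first.

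Much of this stands, and it rules out three stronger readings that a reader might infer:

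- **Every child at the top score is deleted.** The model uses visit records. An undefined value removes that visit, and a child leaves only if every visit is at a limit. Even that is a software consequence of the printed formula, not a stated rule.
- **The logit model is bound to become primary.** The fallback is conditional on clear non-normality, and the sentence does not name the choice of scale.
- **Back-transformation contradicts Table 1.** The wording does not say that a mean logit is inverted. Averaging predictions on the T-score scale would fit it. The method is under-specified, which is not a demonstrated mismatch.

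The objection does not rescue the formula or the rule. The only printed formula fails at both limits of a scale that the SAP closes at 10 and 58. The text compares original-scale and logit-scale fitting immediately before the likelihood sentence, so a cross-scale comparison is its natural reading.

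**Conclusion.** Two parts of a conditional fallback for the primary outcome give a wrong result if followed as written. The rescaling leaves the logit undefined at the limits. The log-likelihood rule, on its natural reading, favours the logit almost regardless of fit. The first is certain from the formula. The second is certain mathematically and depends on that reading of an incomplete sentence.

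The effect on the trial is not known. It ranges from small (1.5% v 6.7% of 12-month records, power above 99%) to serious (21% v 34%, single-visit power about 43%). These figures assume normal scores cut at 58 and literal deletion, and the repeated-measures loss should be smaller. With an endpoint squeeze the deletion problem disappears. The documents do not support saying that the primary result will be biased by a given amount. They do support correcting the text before the analysis.

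**What to change.** Amend SAP 6.2 as follows:

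1. Use fixed limits 10 and 58, with u = (y − 10)/48. Before the logit apply a stated squeeze such as (u(N − 1) + 0.5)/N, so that no record is dropped. Define N in advance: the top score maps to a logit of about 6.3 with N = 266 and 8.1 with N = 1670 (334 × 5 records).
2. Complete the likelihood sentence. Either do not choose the scale by likelihood, or subtract Σ log[48 × u*(1 − u*)] from the logit-scale value, where u* is the squeezed value (the squeeze adds only a constant), and compare on an identical set of records. Comparison of models on one scale can stay.
3. State that the treatment effect is the difference in averaged predictions on the T-score scale at 12 months, to match Table 1.
4. Reconcile this fallback with the unadjusted non-parametric tests in Protocol 10.1, and say which applies.

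Keeping the T-score model primary with robust standard errors, and the logit model as a sensitivity analysis, is a reasonable option but not a requirement. The cost is SAP wording and a few lines of code, with no new data.

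### If the fallback logit transformation in SAP 6.2 is used, the printed rescaling formula leaves every PROMIS observation at the minimum or maximum without a value

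*SAP*

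**What the plan says.** SAP 6.1 describes the primary outcome in these words: "This is a bounded score on a standardised scale (T-score) in the interval" from 10 to 58, with both ends included.

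SAP 6.2 fits the primary linear mixed model to the T-score, "including all available data on randomised participants, at all-time points up to and including 12 months". Under model checking it adds a fallback: "data transformation will be considered if model assumptions (particularly normality of residuals) are clearly violated". In that case the outcome is rescaled and logit-transformed, and the analyst is to "proceed fitted the same mixed effects linear model described above on the transformed scale", with effects back-transformed to the original scale.

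The rescaling is introduced with "Data will be first transformed to a (0, 1) scale" and written out as "transformed y_new=(γ -min(γ))/(max(γ)-min(γ)), where γ represents the outcome". A methods paper is cited (SAP reference 33). The text does not say whether the minimum and maximum are the scale limits or the sample extremes. It gives no adjustment for scores at either end.

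The same part of 6.2 suggests that the logit model may be preferable because it should stabilise the variance. It proposes to choose among a few competing models by log-likelihood.

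**The concern.** The logit is finite only strictly between 0 and 1. The formula reaches both ends, so it does not deliver the open scale that the sentence promises, and observations at an end have no transformed value.

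The observations lost are the highest and lowest scores. If recovered children gather at 58, the better arm loses more of its 12-month values, which pulls the arms together. Loss that depends on the value itself is not missing at random, and missing at random is the assumption behind the primary model (SAP Table 1 and 6.3). These losses would also not appear in the drop-out tables, because the answers were collected.

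The likely trigger makes this worse. Pile-up at a cap is a typical cause of clear non-normality on a bounded score, so the fallback is most likely to be invoked when many scores sit at the bound.

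Model choice is affected too. A log-likelihood from a model that has lost observations cannot be set against one from a model that has not. A change of scale needs a Jacobian term in any case, but that term does not repair a difference in the data used.

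**Working it through.** **1. The plan's own figure.** For a 4-point difference, SD 10, two-sided 5% and 90% power (SAP 3.3), the t-test calculation gives 132.3, so 133 per arm and 266 in total. With 20% loss, 133/0.8 = 166.25, so 167 per arm and 334 in total. Both agree with the plan. By the normal formula, power with 133 per arm is 90.4%.

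**2. The formula at the scale bounds.** Let u = (y − 10)/48 and logit = ln[u/(1 − u)].

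| Score | u | logit |
|---|---|---|
| 10 | 0 | minus infinity |
| 10.5 | 0.0104 | −4.55 |
| 34 | 0.5 | 0 |
| 57.5 | 0.9896 | 4.55 |
| 58 | 1 | plus infinity |

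**3. The formula with sample extremes.** The lowest observed score always gives u = 0 and the highest always gives u = 1. At least one observation at each end is therefore undefined, whatever the data. The whole scale also hangs on those two extremes.

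**4. Illustration of size (assumed, not from the documents).** Take normal latent scores capped at 58, a true latent difference of 4, and z = (58 − mean)/SD.

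- Share at the cap: 1 − Φ(z).
- Mean with capped scores kept: mean − SD × [φ(z) − z(1 − Φ(z))].
- Mean with capped scores removed: mean − SD × φ(z)/Φ(z).

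For SD 10 and means 50 and 54, z = 0.8 and 0.4:

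- Shares at the cap are 0.212 and 0.345 (0.3446 before rounding), so 21% and 34%.
- With capped scores kept, the means are 48.80 and 51.70, a difference of 2.90.
- With them removed, the means are 46.32 and 48.38, a difference of 2.06.
- Scores left at 12 months: 133 × 0.788 + 133 × 0.655 = 105 + 87 = 192 of 266.

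Other assumptions give a wide range:

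| Means, SD | Share at cap | Raw difference, kept | Raw difference, removed |
|---|---|---|---|
| 45 and 49, SD 6 | 1.5%, 7% | 3.86 | 3.40 |
| 45 and 49, SD 10 | 10%, 18% | 3.45 | 2.64 |
| 50 and 54, SD 6 | 9%, 25% | 3.35 | 2.52 |
| 54 and 58, SD 10 | 34%, 50% | 2.31 | 1.64 |

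**5. Loss of numbers alone.** With a 4-point difference and SD 10, losing 10%, 20% or 30% of the 266 twelve-month scores lowers power from 90% to 87%, 83% or 78%.

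**6. Why the repair must be fixed in advance.** The transformed value of a score of 58 depends strongly on the adjustment chosen.

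- Bounds widened by 0.5 point (9.5 and 58.5): ln(48.5/0.5) = 4.57.
- Bounds widened by 1 point (9 and 59): ln(49/1) = 3.89.
- Shrinkage of the form [u(N − 1) + 0.5]/N: ln(2N − 1), which is 6.27 for N = 266 and 7.89 for N = 266 × 5 = 1,330 observations.

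**The case against.** A reader might infer that every child at the top score drops out of the primary analysis. The documents do not support that, for two reasons.

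- **The step is conditional.** SAP 6.2 notes that mixed models tolerate small departures from normality, and it keeps an original-scale model with heteroscedastic residuals as an option. The default analysis on the T-score loses nothing.
- **The model loses observations, not children.** It uses up to five occasions per child, so a child at 58 at 12 months still contributes visits that are not at a bound. The 192 of 266 above counts 12-month scores.

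The size is also unknown. The only statement about ceilings (Protocol 6.3) is that the adaptive test showed none in children with congenital limb abnormalities. Children answer different items, so a cluster at exactly 58 is an assumption. Protocol 7.2 and SAP 3.3 expect an SD below 10. The 2.9-to-2.1 shrinkage is a raw mean difference, not a back-transformed estimate from a model that borrows from other visits.

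Finally, the cited paper may contain an end-point adjustment. Undefined values would also probably be noticed through the blinded review (SAP 3.6), the data checks (5.6) or the independent repeat of the primary model (7).

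All of this limits the claim but leaves its core intact. The congenital limb population is not children a year after an acute fracture. The cited paper cannot be checked here, and an analyst or validator would code the formula as printed, which contains no adjustment. The quality checks might reveal missing values but supply no rule for them, so any repair would be chosen after the data had been seen.

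**Conclusion.** The formula is wrong as written. On either reading of minimum and maximum it produces values of exactly 0 or 1, which contradicts the stated scale and leaves the logit undefined there. If the fallback is used, observations are lost according to their value, possibly at the primary time point. That conflicts with the commitment to analyse all available data, and it invalidates log-likelihood comparison with the untransformed model.

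The undefined end points follow from the SAP alone. The extent of loss does not. Across the scenarios shown, 1.5% to 34% of 12-month scores in one arm and 7% to 50% in the other would go, and the raw difference shrinks each time. All of these rest on an assumed capped normal distribution and a 4-point latent difference.

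Because the step is conditional, this ranks below the faults that must be corrected for the default primary analysis to stand. It should still be repaired before database lock.

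**What to change.** In SAP 6.2, under model checking:

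1. Replace the sample-based minimum and maximum with fixed bounds just outside the instrument range, for example 9.5 and 58.5. Another pre-specified end-point adjustment would do if it keeps every score strictly between 0 and 1.
2. State that no observed score may be lost through the transformation.
3. Repeat the fallback analysis with alternative offsets, for example 0.5 and 1 point, and report both.

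The cost is a line or two of SAP text and one extra model run. The drawback is that the offset is arbitrary and moves the end-point logit considerably, which is why the repeat is needed. Dropping the transformation altogether is a separate choice of analysis and is not needed to repair this formula.
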